### 6.3. Demographic and Baseline Characteristics

### 6.3.1. Demography and Race

Demographic characteristics (age, sex, ethnicity, height, weight and body mass index) will be summarised and listed.

The proportion of subjects reporting each race and racial combination will be presented. Race will also be listed.

### 6.3.2. Baseline Lung Function Tests

The following Baseline (as defined for this study) clinic lung function results will be summarised:

- Pre-bronchodilator FEV1 (mL)
- Pre-bronchodilator percent predicted FEV1 (%)
- Pre-bronchodilator Forced Vital Capacity (FVC) (mL)
- Pre-bronchodilator FEV1/FVC

### 6.4. Medical Conditions

An update in each subject's medical history since the medical history form in the MEA115661 trial will be collected at Visit 1. If a subject reports no change in medical history, the respective subject's medical history information will be copied over from the MEA115661 trial.

The proportion of subjects who report medical conditions in each medical condition class will be presented, for past and current conditions separately.

### 6.5. Concomitant Medications

The proportion of subjects reporting each concomitant medication will be presented. Multi-ingredient medications will be presented according to their combination ATC classification rather than the classifications of the ingredients. Summaries will be split into asthma and non-asthma concomitant medications, as well as into those taken during treatment and post-treatment (as described in Appendix 3: Treatment Phases). Asthma medication outputs will not display ATC grouping.

Classification of a medication as during or post-treatment will be made with reference to the study treatment start and stop dates and the medication start and stop dates. If the medication start date is missing or partial then the medication will be considered on-treatment unless there is evidence to the contrary (e.g. the month of the start date is present and is less than the month of the first dose of study medication).

A listing of the relationship between ATC level 1, ingredient and verbatim term will be produced.

### 6.6. Protocol Deviations

Important protocol deviations will be summarised and listed for the AT Population. More details are in Appendix 10: List of Data Displays.

### 7. SAFETY ANALYSES

The main interest of the study is to investigate the long-term safety and these analyses will be based on the As Treated (AT) population, unless otherwise specified.

### 7.1. Extent of Exposure

The number of treatments administered and the time spent on-treatment will be summarised and listed.

Additionally, the overall exposure will be summarised from study 201312 and preceding mepolizumab studies where the same subjects participated (MEA115588, MEA115575 and MEA115661).

### 7.2. Adverse Events Analyses

Adverse events analyses including the analysis of adverse events (AEs), Serious (SAEs) and other significant AEs will be based on GSK Core Data Standards.

AEs occurring during pre-treatment, on-treatment and post-treatment phase will be summarised separately. Adverse events will be coded using the latest version of the Medical Dictionary for Regulatory Activities (MedDRA).

The number and percentage of subjects experiencing at least one AE will be summarised. Exposure adjusted rates of AEs will also be presented to account for the length of exposure within the trial. For the definition of exposure adjusted AEs, see Appendix 5: Derived and Transformed Data.

The details of the planned displays are provided in Appendix 10: List of Data Displays.

### 7.3. Adverse Events of Special Interest Analyses

Adverse events of special interest (AESIs) are adverse events associated with the identified and potential risks of mepolizumab. AESIs of anaphylaxis reactions, systemic reactions, and local injection site reactions are collected via targeted eCRF within the study. Events captured on the eCRF as systemic reactions will be further categorized as allergic/hypersensitivity reactions or non-allergic reactions. Events with preferred terms such as injection related reaction or administration related reaction will be considered non-allergic reactions. All remaining events will be considered allergic/hypersensitivity reactions.

AESIs of opportunistic infections, malignancies, serious CVT events and serious ischemic events will be identified from a list of relevant preferred terms maintained within a project level reference dataset created based on the MedDRA dictionary available at the time of database freeze for this study, further details of how relevant preferred terms are identified are given in the Program Safety Analysis Plan (PSAP).

Separate summary tables showing the number and percent of subjects with each type of AESI, broken down by preferred term will be created. Information will be reported as part of the standard AE tables for AESIs of infections, serious infections, neoplasms, cardiac disorders and serious cardiac disorders.

For each type of AESI a profile summary table will be produced containing information which would include, but not be limited to, the number of occurrences of the event, event characteristics, time to onset, intensity, outcome and action taken.

A listing of any subjects with systemic events identified by the investigators as meeting the criteria for anaphylaxis as outlined by the 2006 Joint National Institute of Allergy and Infectious Disease/Food Allergy and Anaphylaxis Network Second Symposium on Anaphylaxis [Sampson, 2006] will be provided. Adverse events experienced on a day of dosing will be summarised and presented by SOC and preferred term.

Cardiovascular events will also be captured on targeted CV event pages of the CRF following AEs and SAEs. The following cardiovascular event listings will be produced for all investigator reported events:

- Myocardial infarction/unstable angina
- Congestive heart failure
- Arrhythmias
- Valvulopathy
- Pulmonary hypertension
- Cerebrovascular events/stroke and transient ischemic attack
- Peripheral arterial thromboembolism
- Deep venous thrombosis/pulmonary embolism
- Revascularization

Equivalent listings will be produced for all CEC adjudicated events. Note that Arrhythmias, pulmonary hypertension, revascularisation and valvulopathy events will not be sent for adjudication by the CEC, hence for such events listings will only be produced for investigator reported events.

Summaries of events which were reported and confirmed (or not) as cardiovascular following adjudication by the trial Clinical Endpoint Committee (CEC) will be summarised.

The details of the planned displays are provided in Appendix 10: List of Data Displays.

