After giving informed consent for this study, eligibility will be assessed via multiple evaluations, including physical examination, vital signs, electrocardiogram (ECG), and an updated medical history. Subjects whose health status remains appropriate for the study will then be assessed based on the inclusion and exclusion criteria. Those subjects meeting all of the eligibility requirements will receive their first dose of mepolizumab at Visit 1. Mepolizumab will be administered approximately every 4 weeks with the last dose at Week 168 (Visit 43). Forty three doses will provide therapeutic coverage for 172 weeks (4 weeks following the last dose). Subjects will then continue to receive mepolizumab 100mg SC injections for up to 172 weeks or until one of the following occurs:

- the risk/benefit profile for the subject is no longer positive in the opinion of the investigator **or**
- the subject's physician withdraws the subject **or**
- the subject withdraws consent **or**
- the sponsor discontinues development of mepolizumab **or**
- the sponsor discontinues the study in the relevant participating country **or**
- mepolizumab becomes commercially available in the local country.

The study closure process will begin, on a country by country basis, as mepolizumab becomes commercially available for prescription. Some subjects will complete the original 120 week treatment period (as specified in the previous protocol) prior to mepolizumab being available for prescription. To ensure these subjects do not have a treatment gap the treatment period will be extended for an additional 52 weeks to a total of 172 weeks.

Subjects will remain on standard of care asthma therapy throughout the study. Asthma medication may be adjusted at any time during the study at the discretion of the investigator. All changes in asthma therapy will be captured in the source documents and the electronic case report form (eCRF). At each clinic visit, adverse events will be assessed and subjects will be questioned regarding the occurrence of any exacerbations since their last clinic visit. The Asthma Control Questionnaire-5 (ACQ-5) will be performed every 12 weeks during the study and at the Exit/Early Withdrawal Visit to assist the investigator in monitoring the subject's asthma status along with spirometry assessments every 6 months and at the Exit/Early Withdrawal Visit.

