4. SUBJECT SELECTION AND WITHDRAWAL CRITERIA

4.1. Number of Subjects

Approximately 375 subjects are estimated to be eligible to take part in this study. As the study is open-label, no randomization will occur. Attrition/withdrawal is expected to be less than 10% of enrolled subjects.

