6.3.10.3. Vital Signs

Sitting pulse rate and blood pressure measurements will be performed by the investigator or qualified site staff as outlined in Time and Events Table ([Appendix 1 Time and Events Table](#)). Measurements will be done pre-injection with the subject sitting, having rested in this position for at least 5 minutes before each reading. They will be taken before measurement of any clinic lung function tests or ECGs at the specified time point.

At the baseline visit, height and weight will also be measured.

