### 11.3.2. Treatment Phases (Adverse Events)

Adverse events will be classified according to time of occurrence relative to the first and last date of the study treatment in study 201312.

Treatment Phase	Definition
Pre-Treatment	AE Onset Date & time < First dose of mepolizumab in study 201312 If mepolizumab treatment in study 201312 is never started then all AEs will be
	classified as pre-treatment.
On-Treatment	First dose of mepolizumab in study 201312 $\leq$ AE Onset Date & Time $\leq$ Last dose of mepolizumab in study 201312 + 28 Days.
	If an AE start date is missing or partial then the AE will be considered on-treatment unless there is evidence to the contrary (e.g. month/year of onset date is present and is earlier than the month/year of First dose of mepolizumab in study 201312).
Post-Treatment	AE Onset Date & time > Last dose of mepolizumab in study 201312 + 28 days

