### 11.5.4. Safety

#### Extent of Exposure

- Number of days of exposure to study drug will be calculated based on the formula: Duration of Exposure in Days = Last mepolizumab dose in study 201312 – (First mepolizumab dose in study 201312) + 29 days
- The extent of exposure will also be summarised as the number of study treatments administered

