### 11.10.6. Safety Tables

Safety:	Safety: Tables							
No.	Population	IDSL / Example Shell	Title	Programming Notes	Deliverable			
Exposu	re							
2.1.	AT	SHELL	Summary of Exposure to Study Medication	ICH E3 See format of Study Population Table 1.28 (200862 'final' reporting effort).	SAC			
2.2.	AT	SHELL	Summary of Exposure to Study Medication (Therapeutic Coverage) From Studies MEA115588, MEA115575, MEA115661 and 201312	See format of Study Population Table 7.74 (MEA115661 'manuscript1' reporting effort).	SAC			
Advers	e Events (AEs)							
2.3.	AT	SHELL	Overview of Adverse Events		SAC			
2.4.	AT	AE1	Summary of On-Treatment Adverse Events by System Organ Class and Preferred Term	ICH E3	SAC			
2.5.	AT	SHELL	Summary of Exposure Adjusted On-Treatment Adverse Events by System Organ Class and Preferred Term		SAC			

Safety:	Safety: Tables							
No.	Population	IDSL / Example Shell	Title	Programming Notes	Deliverable			
2.6.	AT	AE5	Summary of On-Treatment Adverse Events by Maximum Intensity by System Organ Class and Preferred Term	ICH E3 Add a Total column across all severities	SAC			
2.7.	AT	AE1	Summary of Post-Treatment Adverse Events by System Organ Class and Preferred Term		SAC			
2.8.	AT	AE5	Summary of Post-Treatment Adverse Events by Maximum Intensity by System Organ Class and Preferred Term	ICH E3 Add a Total column across all severities	SAC			
2.9.	AT	AE3	Summary of Common (>=3%) On-Treatment Adverse Events by Overall Frequency	ICH E3 ≥3% (prior to rounding to nearest percent)	SAC			
2.10.	AT	SHELL	Summary of Exposure Adjusted On-Treatment Common (>=3%) Adverse Events by System Organ Class and Preferred Term	≥3% (prior to rounding to nearest percent)	SAC			
2.11.	AT	AE1	Summary of On-Treatment Drug-Related Adverse Events by System Organ Class and Preferred Term	ICH E3	SAC			
2.12.	AT	SHELL	Summary of Exposure Adjusted On-Treatment Drug-Related Adverse Events by System Organ Class and Preferred Term		SAC			
2.13.	AT	AE5	Summary of On-Treatment Drug-Related Adverse Events by System Organ Class and Preferred Term and Maximum Intensity	Add a Total column across all severities	SAC			
2.14.	AT	AE1	Summary of Adverse Events Reported on Day of Dosing by System Organ Class and Preferred Term		SAC			
2.15.	AT	SHELL	Summary of On-Treatment Adverse Events by Age Group (12- 17, 18-64, >=65 years)		SAC			
2.16.	AT	SHELL	Summary of On-Treatment Adverse Events by Highest Anti Drug Antibody Result At Any Time Post Baseline		SAC			

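### The dosing-day adverse event table (SAP Table 2.14) has no rate for other days and no rule on order relative to the injection, so by itself it cannot indicate acute reactions

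*SAP*

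**What the plan says.** SAP 7.3 ends its paragraph on the anaphylaxis listing with: "Adverse events experienced on a day of dosing will be summarised and presented by SOC and preferred term". The display list in SAP 11.10.6 implements this as Table 2.14, "Summary of Adverse Events Reported on Day of Dosing by System Organ Class and Preferred Term", for the As Treated population on a standard AE shell, with the programming-notes column blank. The text speaks of events *experienced* on the day, the title of events *reported* on it.

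Four other provisions bear on what enters the table:

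- **Timing relative to dose.** SAP 11.3.2 sorts AEs into phases against the first dose and the last dose plus 28 days; its pre-treatment rule is "AE Onset Date & time < First dose of mepolizumab in study 201312". Neither document orders an event against the injection of the same day for later doses.
- **Findings before the injection.** For vital signs, Protocol 6.3.10.3 says "Measurements will be done pre-injection with the subject sitting". Protocol 6.3.10.1 has laboratory samples taken before dosing. Under Protocol 6.3.3, abnormalities judged clinically significant are recorded as AEs.
- **When AEs are asked about.** Protocol 3.1: "At each clinic visit, adverse events will be assessed". Dosing takes place at those same visits.
- **Imputed dates.** SAP 11.6.2.1 moves some partial onset dates to the treatment start date, which is a dosing day.

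SAP 7.2 promises exposure-adjusted AE rates, and several tables carry them (for example 2.5, 2.10 and 2.12). Table 2.14 is not among them.

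**The concern.** In a single-arm study, a count of dosing-day events can be read only against the count expected on any other day. A subject treated for two or three years has dozens of dosing days, and ordinary colds, headaches and back pain will start on some of them. Without a reference, a long list of preferred terms looks the same whether or not the drug causes acute reactions, and it lengthens as follow-up lengthens. With no order rule, an event that began before the injection, or an abnormality found at the pre-injection check, counts like one that followed it.

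This matters because Table 2.14 is the one display of same-day events that does not depend on the investigator calling the event a reaction or drug-related. It could bring an unrecognised reaction to light, but only if background can be told apart from excess.

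**Working it through.** **1. The plan's own figures.** Protocol 3.1: "Forty three doses will provide therapeutic coverage for 172 weeks (4 weeks following the last dose". Dosing every 4 weeks from Week 0 to Week 168 gives 168/4 + 1 = 43 doses, and 43 × 4 = 172 weeks. Both figures reproduce. The SAP 11.5.4 exposure formula (last dose minus first dose plus 29 days) gives 168 × 7 + 29 = 1205 days. Dosing days are 43/1205 = 3.6% of exposure, about one day in 28.

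**2. Assumed inputs.** The documents give no AE rate. They give no count of treated subjects either, only "Approximately 375 subjects are estimated to be eligible to take part in this study". SAP 11.6.1 expects no subject to complete the schedule. I therefore assume N = 340 treated subjects, 26 doses each (25 × 28 + 29 = 729 exposure days, of which 26 are dosing days and 703 are not), a constant background of L = 2 to 6 AEs per subject-year, and no drug effect.

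**3. Chance content of the table.** Expected dosing-day AEs per subject: m = L × doses/365.25. Expected events: N × m. Share of subjects with at least one: 1 − exp(−m).

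| Doses | L per year | m | Events | Subjects in table |
|---|---|---|---|---|
| 26 | 2 | 0.142 | 48 | 13% |
| 26 | 6 | 0.427 | 145 | 35% |
| 43 (maximum) | 2 | 0.235 | 80 | 21% |
| 43 (maximum) | 6 | 0.706 | 240 | 51% |

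**4. Single terms.** A preferred term with a background of 0.1 per subject-year has an expected 340 × 0.1 × 26/365.25 = 2.4 chance events, so it appears with probability 1 − exp(−2.4) = 91%. At 0.2 per year this is 99%.

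**5. Rates that differ between subjects.** With gamma-distributed rates (dispersion k), the share is 1 − (1 + k·m)^(−1/k). At 26 doses and L = 6, k = 1 to 2 gives 30% to 27% in place of 35%. At 43 doses it gives 41% to 36% in place of 51%. The expected number of events does not change.

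**6. Order rule alone.** If onset is uniform over the day and the injection falls between 08:00 and 14:00 (both assumptions), 8/24 = 33% to 14/24 = 58% of dosing-day onsets precede it. For an injection at 10:00, keeping only later onsets leaves 48 × 14/24 = 28 to 145 × 14/24 = 85 chance events at 26 doses. An order rule thins the background but does not remove it, so a reference rate is needed as well.

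**7. What a reference would show.** With no acute effect and no date heaping, dosing days and other days would both run at L/365.25, that is 5.5 (L = 2) to 16.4 (L = 6) events per 1000 subject-days.

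**The case against.** The strongest reply is that Table 2.14 is supplementary. Systemic, local and anaphylactic reactions are collected on a targeted eCRF and reported in Tables 2.34 to 2.41 and Listings 17 to 20, with profile tables that include time to onset. Drug-related AEs have Tables 2.11 to 2.13. The study has no hypotheses and its safety summaries are descriptive. This stands. A reader might infer that acute reactions have no proper analysis here, or that a real excess would necessarily go unseen; the documents support neither. Two limits remain: those displays rest on investigator judgement in an open-label study, and the only onset derivation in SAP 11.3.2.1 counts days from the first dose, not from the latest injection.

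Second, a rough benchmark can be worked out: the Table 2.5 rate per subject-year, times total doses, divided by 365.25. Dosing days are only 3.6% of exposure, so their inclusion in Table 2.5 matters little. This also stands. What is missing is a planned side-by-side display.

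Third, the SAP does not call the table a screen for acute reactions, and it does not state the entry rule; shells are available only on request. That is correct. I take onset on the dosing date as the natural reading of *experienced*. If *reported* governs, the table could take in events from the whole interval before each visit.

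Fourth, AEs are elicited on dosing days, so onset dates may heap there and push up a dosing-day ratio even with no drug effect. This is the most serious objection to a headline rate ratio with a confidence interval. Such a ratio might also be presented as a well-powered test. For a true ratio of 1.5 and 48 background events, however, a normal approximation for Poisson counts gives 79% to 93% power depending on the variance used, and about 66% if variance is doubled for clustering. It should not carry inference.

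Fifth, the contribution of pre-injection findings is unknown. Vital signs are taken at every visit but safety bloods only about every 24 weeks, and only clinically significant results become AEs.

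**Conclusion.** The point holds as a matter of interpretability. Table 2.14 mixes background with any acute reactions, its content grows with the doses received, and nothing planned beside it separates the two. Under the assumptions in step 2 the chance content at 26 doses is about 48 to 145 events and 13% to 35% of subjects, somewhat fewer subjects if AE rates vary between them. The size depends on an AE rate, a number of subjects and a dose count that the documents do not give. That some background enters the table does not depend on those values.

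A reader might be drawn to the figure of a fifth to a half of subjects (21% to 51%). That is the full 43-dose schedule with identical AE rates in all subjects, and SAP 11.6.1 says no subject will complete. It is an upper scenario, not the expected picture.

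The change is worth making because it is cheap. It does not affect the main analysis of the reaction endpoint.

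**What to change.** In SAP 7.3 and the programming note for Table 2.14:

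1. Define entry as AE onset on the date of any dose, and use the same word in text and title. Flag separately events with onset time before that day's injection, events with missing onset time, and events whose onset date was imputed to the first-dose date.
2. Show, overall and for common preferred terms, events per 1000 subject-days in three rows for the same subjects: dosing days, a pre-specified few days just after dosing, and the remaining on-treatment days.
3. Footnote that dosing days are visit days, so onset dates may heap on them. Treat the days just after dosing against the remaining days as the less biased contrast. Any ratio or subject-clustered confidence interval is descriptive only.

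Cost: SAP wording and one extra derived table. The rates need only dosing and onset dates. The flag for order needs clock times; SAP 11.3.2 refers to onset date and time, but the documents do not establish that times are recorded for every event and every injection, hence the separate missing-time flag. The first contrast keeps some visit-day heaping, and the second can miss reactions confined to the dosing day, so both should be shown.

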### 7.4. Clinical Laboratory Analyses

Laboratory evaluations including the analyses of Chemistry laboratory tests, Hematology laboratory tests, and liver function tests will be based on GSK Core Data Standards. The details of the planned displays are in Appendix 10: List of Data Displays.

### 7.5. Other Safety Analyses

The analyses of non-laboratory safety test results including ECGs and vital signs will be based on GSK Core Data Standards, unless otherwise specified. The details of the planned displays are presented in Appendix 10: List of Data Displays.

### 7.5.1. Immunogenicity

Immunogenicity is a measure of the immune response to a therapeutic drug (e.g. a monoclonal antibody) resulting in generation of anti-drug antibodies. Clinical samples are tested in a sequence of binding anti-drug antibody (ADA) and neutralising antibody assays:

- a) Screening assay. Each sample is tested for the presence of anti-drug antibodies (ADA assay) and initially declared positive or negative according to assay cut-off criteria. Negative samples are not tested further. Positive samples are then tested in the confirmation ADA assay.
- b) Confirmation assay. Each positive sample from the screening assay is either confirmed positive in this assay (ADA assay), or is declared negative and are not tested further. Positive ADA samples are then tested in the titer assay and neutralization (NAb) assay.
- c) Titration assay. Each positive sample from the ADA confirmation assay is serially diluted to provide a titre, corresponding to the highest dilution factor that still yields a positive test result.
- d) Neutralising assay. Each positive sample from the ADA confirmation assay is tested with the neutralising antibody assay and found as either positive or negative in this assay (NAb assay).

The mepolizumab ADA (screening/confirmation/titration) assay version 2011N122789\_03 is performed at Alliance Pharma (method 120711M01.V02). The mepolizumab Nab assay version 2011N129752\_03 is being performed within GSK.

- A table will be produced summarising the number and percentage of negative and confirmed positive subjects ADA samples by visit in the AT population. The table will also summarise the highest assay result obtained post-baseline for each subject.
- A similar table will also be produced summarising results for the neutralising antibody assay in the AT Population, by visit.
- An additional summary of treatment emergent positive confirmatory binding antibody assay and results in the subset of subjects who did not have a positive confirmatory binding antibody assay result prior to the first dose of study treatment will also be presented.
- All immunogenicity results (i.e. ADA screening and confirmatory assay results, titre values and neutralising antibody results) will be listed.

The details of the planned Immunogenicity displays are presented in Appendix 10: List of Data Displays.

